- Baseline Visit date (defined as the start date of all Baseline testing) must be no later than 2 weeks after receiving confirmation of meeting **final study cohort criteria** from the CGA (and if possible, within 90 days of the Screening Visit date). All Baseline testing must be completed within 7 days of the Baseline Visit date, except PROs as specified
- All Follow up visit testing must be completed on the same day, except PROs as specified
- If ERG has been undetectable in the past, no need to perform at baseline, at investigator's discretion
- If ERG is undetectable at baseline, no need to perform at 48M, at investigator's discretion
- For static perimetry and microperimetry, all Vision Cohort 1 and 2 participants will complete two tests at baseline. The results will be compared according to the **visual field criteria** (section 3.2) to determine if a third test is needed.
- Kinetic VF III4e performed within the last 18 months prior to or including the Screening Visit date for Vision Cohort determination only
- Ophthalmic exam includes slit-lamp biomicroscopy, indirect ophthalmoscopy and intraocular pressure (IOP). IOP measurements will be taken prior to pupil dilation. Whenever possible the site should make its best effort to ensure that the exam takes place at approximately the same time of the day at each visit and with the same equipment
- PROs will be completed by participants who agree to answer these additional questions; may be completed in person or remotely any time within 6 months after Baseline or +/- 6 weeks of 24 or 48-month follow-up visits
- If the Baseline visit date is more than 90 days after the Screening Visit date, all Visual acuity procedures must also be completed

Visit Schedule for Vision Cohort 3

Visit	Screening	Baseline	12M	24M	36M	48M
Visit Target Windows	(up to Day -90) ^a	(Day 0) ^b	Wk 52 ± 4 (Phone call only)	Wk 104 ± 4 (Phone call only)	Wk 156 ± 4 (Phone call only)	Wk 208 ± 4 ^c
Participant-Level Procedures						
Informed Consent	X					
Demographics/Medical History (including pre-existing conditions, patient-reported daily activities and medications)	X					
Physical Exam (including height, weight and blood pressure)		X				
Concomitant Medications/Adverse Events		X	X	X	X	X
Patient Reported Outcomes (ULV-VFQ-50, PROMIS®-29, MRDQ and ViSIO-PRO) ^f		X				X
Ocular Procedures - All testing performed in each eye						
Complete Ophthalmic Exam ^e	X					X

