 772 detect differences as small as 10% if SD is within 20%. With a sample size of 65 (effective
 773 sample size N= 72), there will be at least 55% power to detect differences as small as 10% if SD
 774 is within 20%.

775 For objective 4 of evaluating variability and symmetry, a sample size of 90 participants for
 776 Vision Cohorts 1 and 2 will have a 95% CI of (0.34, 0.63) when observed r equals to 0.5, and
 777 (0.72, 0.86) when observed r equals to 0.8. With a smaller sample size of 65 participants, the
 778 95% CI would be (0.30, 0.66) when observed r equals to 0.5, and (0.70, 0.87) when observed r
 779 equals to 0.8. This is considered acceptable precision to meet our objective.

780 **6.2 Data Analysis**

781 The analysis plans below are written with respect to the majority of outcomes of interest.
 782 Analyses will include data on both eyes for each participant, and models and confidence
 783 intervals will adjust for correlation between 2 eyes of the same participant.

784 **6.2.1 Primary Objectives Analyses**

785 The primary objectives of the natural history study and brief analysis plan for each are as
 786 follows.

- 787 1. Characterize the natural history of retinal degeneration associated with biallelic
 788 pathogenic mutations in the *EYS* gene over 4 years, as measured using functional,
 789 structural, and PRO measures
 - 790 a. Analysis plan for functional and structural measures: The distribution of each
 791 outcome at each visit will be summarized (including tabulating categorically, as
 792 well as means, SDs, medians, quartiles, ranges; both the absolute change and
 793 percent change will be evaluated, tests performed multiple times will be analyzed
 794 using average of all available tests). To determine the average annual rate of
 795 progression in the population for each outcome, a repeated measures least squares
 796 regression model will be fit using all available outcome data at baseline and all

797 annual visits. Multiple imputation will be used to impute the outcome values for
 798 all missing time points (including participants who discontinue follow up prior to
 799 48 months). Secondary analyses using binary definitions of outcome measures
 800 will also be explored in time to event analyses; Kaplan-Meier estimates with 95%
 801 confidence intervals will be calculated. Mixed effects linear models for the
 802 continuous outcome measures and for the time-to-event analyses will also be

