 834 analysis of covariance (ANCOVA) models (adjusting for baseline). A stepwise
 835 selection procedure will be used to build the final model. A threshold of $P < 0.10$
 836 will be used to add to the model, and a threshold of $P < 0.01$ will be used to remain
 837 in the multivariate model. Missing outcome data will be imputed using multiple
 838 imputation as noted in the primary analysis. Linearity of continuous factors will
 839 be assessed and possibly quadratic or cubic terms will be considered if non-linear.
 840 Secondary analyses using binary definitions of outcome measures will also be

- 841 explored in time to event analyses; Cox proportional hazard models will be
 842 evaluated using a parallel stepwise selection procedure.
- 843 • Potential risk factors to evaluate include:
 - 844 ○ Phenotypic:
 - 845 ▪ Clinical diagnosis
 - 846 ▪ Age of onset of initial vision symptoms
 - 847 ▪ Gender
 - 848 ▪ Race/ethnicity
 - 849 ▪ Visual acuity
 - 850 ▪ Lens Status (phakic/pseudophakic/aphakic)
 - 851 ▪ ERG 30 Hz flicker cone amplitudes b-wave (continuous)
 - 852 ▪ FAF pattern as measured qualitatively
 - 853
 - 854 ▪ SD-OCT (as factors related to SP Hill Of Vision (HOV))
 - 855 • Presence of cysts
 - 856 • Central subfield thickness
 - 857
 - 858 ▪ MP
 - 859 • Mean retinal sensitivity
 - 860
 - 861 ▪ SP (as factors related to SD-OCT EZ area)
 - 862 • Volume of 30 degrees HOV
 - 863 • Mean sensitivity
 - 864 • Full field HOV
 - 865 ○ Genotypic:
 - 866 ▪ Characterizations of the variants on the *EYS* protein
 - 867
 - 868 ○ Environmental factors
 - 869 ▪ Smoking status at baseline
 - 870 ▪ Vitamin A use at baseline
 - 871 ▪ Docosahexaenoic acid (DHA) use at baseline
 - 872 ▪ Lutein use at baseline
- 873 4. Evaluate variability of repeat perimetry testing and symmetry of left and right eye
 874 outcomes over 4 years in individuals with biallelic pathogenic mutations in the *EYS* gene
- 875 a. Analysis plan for variability of repeat perimetry testing at baseline: Scatterplots
 876 and Spearman correlation coefficients for pairs (first versus second) of testing
 877 values for each repeated perimetry test. Bland-Altman plots of the inter-eye
 878 difference versus the mean value will be inspected and a linear regression model
 879 for the differences will be used to test whether the slope is 0 and whether
 880 variability changes with greater mean values. The intraclass correlation

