 881 coefficient of the values and the within-person variance will be estimated.

882 b. Analysis plan for the symmetry of left eye versus right eye: At baseline and each
883 subsequent testing time, the symmetry of the test result values from the left and
884 right eyes will be assessed and the symmetry of the change from baseline from the
885 left and right eyes will be assessed for each follow-up visit. Bland-Altman plots of
886 the inter-eye difference versus the mean value will be inspected and a linear
887 regression model for the differences will be used to test whether the intercept is 0
888 and the slope is 0. The intraclass correlation coefficient of the values will be
889 estimated.
890

891 **6.2.2 Sensitivity Analyses**

892 Analyses above will be repeated excluding cases that are not confirmed as pathogenic or likely
893 pathogenic by the Genetics Committee. This will confirm that the results are not influenced by
894 cases that may be ineligible based on genetics expert review but eligible based on clinical
895 review. Exclusions or subgroup analyses may be considered as a result of this analysis.
896

897 **6.2.3 Interim Data Analysis**

898 No formal interim analysis or “stopping guidelines” are planned for determining early stopping
899 according to statistical rules, as no intervention is being studied and thus early efficacy and
900 safety signals are not applicable.

901 Interim analyses will be planned for other reasons, including to evaluate data at baseline and
902 annual visits for reporting in preliminary manuscripts, as well as monitoring data for recruitment
903 and retention benchmarks, and quality assurance throughout the duration of the study. The FFB
904 Consortium Executive Committee will review and oversee these data and their use in reporting.

905

Chapter 7: Data Collection and Monitoring

906 7.1 Case Report Forms and Other Data Collection

907 The main study data are collected on electronic case report forms (eCRFs). When data are
908 directly collected in eCRFs, this will be considered the source data. For any data points for which
909 the eCRF is not considered source (e.g., lab results which are transcribed from a printed report
910 into the eCRF), the original source documentation must be maintained in the participant's study
911 chart or medical record. This source must be readily verifiable against the values entered into

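### Objective 4a sets its Bland-Altman plot and regression on the difference between eyes, not between repeat tests; separately, the correlation intervals in 6.1.4.1 disagree with Table 2

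*Protocol*

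**What the plan says.** Section 6.2.1 divides objective 4 into two parts. Item 4a opens with "Analysis plan for variability of repeat perimetry testing at baseline: Scatterplots", continues with "and Spearman correlation coefficients for pairs (first versus second) of testing" values, and closes with the intraclass correlation: "coefficient of the values and the within-person variance will be estimated". Between these it specifies the agreement analysis: "values for each repeated perimetry test. Bland-Altman plots of the inter-eye" difference against the mean. A linear regression on those differences then tests for zero slope and for variability that changes with the mean.

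Item 4b is the plan for left/right symmetry. It describes its plot in the same terms, "the inter-eye difference versus the mean value will be inspected and a linear" regression fitted, there testing intercept and slope.

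The repeat data come from the baseline visit. The footnote to the visit schedule says of static perimetry and microperimetry that "all Vision Cohort 1 and 2 participants will complete two tests at baseline". Section 3.2 has the site compare test 1 with test 2.

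On the precision of the between-eye correlation, section 6.1.4.1 says of 90 participants: "Vision Cohorts 1 and 2 will have a 95% CI of (0.34, 0.63) when observed r equals to 0.5, and" (0.72, 0.86) at r = 0.8. For 65 participants: "95% CI would be (0.30, 0.66) when observed r equals to 0.5, and (0.70, 0.87) when observed r" is 0.8. Table 2 in section 6.1.3 gives intervals for the same r and n.

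**The concern.** An inter-eye difference compares right with left. It contains true asymmetry between the eyes as well as test error, so it cannot isolate repeatability. Only the Bland-Altman and regression step in 4a examines whether measurement noise depends on the level of sensitivity, and that step is set on the wrong difference. The protocol specifies no Bland-Altman analysis of test 1 minus test 2 anywhere else.

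This matters because the study aims to identify sensitive and reliable outcome measures for later trials. How perimetry noise behaves across the range of sensitivity bears directly on that aim. Read literally, the step would partly duplicate 4b at baseline.

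The second matter is internal consistency: the text and the table give different intervals for the same sample size and the same r.

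**Working it through.** **Part 1: comparison of texts.**

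| | Item 4a | Item 4b |
|---|---|---|
| Stated purpose | repeat perimetry at baseline | left versus right symmetry |
| Scatterplot and Spearman pairs | first versus second test | none specified |
| Bland-Altman difference | inter-eye | inter-eye |
| Regression tests | slope; variability against mean | intercept; slope |

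The purpose and the test pairs in 4a concern repeat testing. The difference it plots and regresses does not.

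A simple model shows why the two differences are not interchangeable. The values here are assumptions, not protocol figures: SD of true sensitivity across participants 5 dB, test error SD 1 dB, and true between-eye correlation ρ of 0.5 to 0.9.

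- SD of test 1 minus test 2, same eye: √(2 × 1²) = 1.41 dB, whatever ρ is.
- SD of right minus left, one test each: √(2 × 5² × (1 − ρ) + 2 × 1²).
  - ρ = 0.5: √27 = 5.2 dB
  - ρ = 0.8: √12 = 3.5 dB
  - ρ = 0.9: √7 = 2.6 dB

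Under these assumptions the inter-eye spread is mostly true asymmetry and changes with ρ, while the repeatability does not.

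**Part 2: the correlation intervals.** Section 6.1.3 uses the Fisher transformation, so the limits are tanh(atanh(r) ± 1.96/√(n − 3)).

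| r | n | Computed | Table 2 | Text of 6.1.4.1 |
|---|---|---|---|---|
| 0.5 | 90 | (0.3267, 0.6407) | (0.33, 0.64) | (0.34, 0.63) |
| 0.8 | 90 | (0.7106, 0.8640) | (0.71, 0.86) | (0.72, 0.86) |
| 0.5 | 65 | (0.2917, 0.6630) | (0.29, 0.66) | (0.30, 0.66) |
| 0.8 | 65 | (0.6909, 0.8735) | (0.69, 0.87) | (0.70, 0.87) |

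All four Table 2 intervals are reproduced. In the text, five of the eight limits differ from Table 2, each by 0.01 and each towards a narrower interval.

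Repeating the formula with the protocol's effective sample sizes:

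- n = 99: (0.3357, 0.6348) and (0.7156, 0.8614), which round to the text for 90 participants.
- n = 72: (0.3035, 0.6557) and (0.6976, 0.8704), which round to the text for 65 participants.

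A search over n = 10 to 299 finds that only n = 99 to 109 reproduces both 90-participant intervals in the text, and only n = 70 to 72 reproduces both 65-participant intervals. Neither range contains the stated number of participants.

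On the Fisher scale the narrowing is 1 − √(87/96) = 4.8% from n = 90 to 99, and 1 − √(62/69) = 5.2% from n = 65 to 72.

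The effective-size multiplier 2/(1 + r) applies to a mean taken over both eyes. A between-eye correlation has one pair per participant, so n is the number of participants, as in Table 2.

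**The case against.** The best defence is that this is a slip of one word. The heading of 4a, its first-versus-second pairs and its within-person variance all point to repeat testing. The regression targets in 4a differ from those in 4b, which suggests 4a was written with repeatability in mind. A statistician would probably read it as intended. Chapter 6 also calls itself a framework for a fuller analysis plan, which may already correct the word. The raw test 1 and test 2 values are collected in any case. Progression analyses average all available tests, so objectives 1 to 3 and the sample size are untouched.

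Most of this stands and limits the weight of the point. It does not remove it. The protocol names the wrong quantity, which is different from leaving a detail to the analysis plan, and a framework that is wrong here can be copied forward.

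On the intervals, it is fair to say that differences of 0.01 decide nothing. The effective-sample-size explanation is only an inference: for 90 participants, Table 2's own n = 100 column gives the same figures as the text, so a misread column fits equally well. No Table 2 column matches the 65-participant text. The correction does not depend on the cause.

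**Conclusion.** The point holds. One step of 4a, the Bland-Altman plot with its regression, is wrong as written because it addresses eye asymmetry under a repeatability heading. Item 4a is mis-specified in part, not void, and no effect on any estimate is claimed. The conclusion rests on the protocol text alone; the dB figures above only illustrate it.

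The interval mismatch also holds as a minor contradiction between text and table. It makes precision look slightly better than it is and leaves the judgement of acceptable precision unchanged. The finding in favour of Table 2 is limited to the four intervals at issue. Overall this should be fixed, and Part 1 is the reason.

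**What to change.** In item 4a, replace the inter-eye difference with the test 1 minus test 2 difference within the same eye, plotted and regressed against the mean of the two tests. Account for two eyes per participant, as section 6.2 already requires. Leave 4b as it is.

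In section 6.1.4.1, restate the intervals from Table 2: (0.33, 0.64) and (0.71, 0.86) for 90 participants, and (0.29, 0.66) and (0.69, 0.87) for 65.

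The cost is a few words and four intervals. No visit, test or data item changes.
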